### Overall Design:

This is a 2.5-year multi-center, prospective, longitudinal, non-drug interventional cohort study to investigate the pattern of COPD disease phenotypes, clinical, humanistic and healthcare utilization burden, disease progression, and management in China. Participants will be recruited from multiple hospitals (excluding tier 1) across Guangdong and Fujian province. In this study, hospitals at prefecture-level and above will be categorized as Type A hospitals; those below prefecture-level will be Type B hospitals. Site/hospital selection will consider pollution level and hospital type representativeness, as well as feasibility of applying digital data capture and hospital data integration.

A wide range of COPD patients across Global Initiative for Chronic Obstructive Lung Disease (GOLD) grade I-IV will be included. Participants with chronic mucus hypersecretion who don't meet the criteria of COPD will be recruited in the chronic bronchitis group. Never smokers without COPD or chronic mucus hypersecretion or chronic respiratory symptoms and without other significant disease burden will be recruited in the healthy control group.

Baseline data will be recorded for all participants at Visit 1 and subjects will be followed up at 6 months and then every 12 months for a total of 2.5 years. Study visits will be conducted within  $\pm$ 30 days of the planned date. In addition to study visits, COPD and chronic bronchitis participants will be contacted by phone on a trimonthly basis within  $\pm$  7 days of the planned date to assess the CAT and collect information on exacerbations and COPD medications; healthy controls will be contacted by phone on trimonthly basis within  $\pm$  7 days of the planned date to assess the CAT only.

A subset of participants from selected Type A hospitals are planned to receive additional assessments including digital monitoring of daily steps; daily digital diary (EXACT/ERS: COPD); monthly CAT; collection of blood for study defined biomarkers; lung HRCT scanning; sputum collection for molecular methods analysis. If moderate/severe exacerbations are reported by the participants or detected by investigators during the acute phase of event, this subset of participants will be invited to site hospital for an exacerbation visit (no more than twice throughout the study). Participants from this sub-cohort constitute the Biomarker and Digital sub-cohort.

In addition, daily air pollution index throughout the study in each participating city will be collected retrospectively from a local environmental monitoring centre.

This cohort study will not provide or recommend any treatment. Patients' diagnosis and treatment will be left to their physicians' judgement and routine practice. Data will be collected from various sources, including electronic case report forms (CRF), EHR from hospital databases, and other electronic sources, such as eCOA, and wearable devices.

### **Number of Participants:**

A total of 2,000 participants are planned to be enrolled, consisting of 1,700 participants with COPD, 180 with chronic bronchitis but without COPD (i.e. without fixed airflow limitation), and 120 never smoker non-COPD healthy controls. COPD subjects will be further classified using the GOLD grades I – IV (i.e. mild, moderate, severe and very severe airflow limitation). To better understand the disease progression of early-stage COPD, i.e. GOLD I and II grades, targets will be set for COPD participants will be recruited in the following manner: GOLD I: 700, GOLD II: 700, GOLD III: 200, GOLD IV: 100. The purpose is to ensure a wide and even spread of the degree of airflow limitation across the study population. The number of participants recruited to each GOLD grade will be monitored and targets adjusted as necessary to ensure an even distribution. Among each GOLD grade and chronic bronchitis group, up to 30% of never smokers will be recruited in each group. All patient population sizes are approximate and allow  $\pm 10\%$  for feasibility.

All participants will be recruited from Type A and Type B hospitals in Guangdong and Fujian province. To represent the difference in patient profile and practice between different hospitals, the ratio of participants from Type A and Type B hospitals will be 2:1. Specifically, healthy control participants will be recruited from the physical examination department at site hospitals. For the healthy control group to be comparable with COPD participants, pre-set criteria on demographic profile (i.e. age, gender) will be specified in detail in the SRM based on previous studies or available real-world data. When appropriate, matching methods will also be used to adjust for differences in baseline factors (e.g. age, gender) in statistical analyses. Matching of the cohorts will be considered to address specific questions, e.g. biomarkers analysis. Methods to achieve balanced cohorts will be chosen based on a hypothesis and the extent of underlying differences between the cohorts and detailed in the main or ad-hoc RAP.

More assessments will be conducted among the 400 Biomarker & Digital sub-cohort participants who will be all recruited only from selected Type A hospitals. The sub-cohort will consist of 50 never smoker healthy control, 100 chronic bronchitis (N never smoker: up to 25), 100 GOLD I (N never smoker: up to 25), 100 GOLD II (N never smoker: up to 25) and 50 GOLD III participants (N never smoker: up to 20). All patient population sizes are approximate and subject to feasibility and the same considerations apply regarding breadth and evenness of spread of severity as apply to the main study cohort.

## 2. SCHEDULE OF ACTIVITIES (SOA)

Study participants will be followed up for 2.5 years and a total of 4 clinic visits (baseline, 6, 18, and 30 months) are scheduled for study assessments with a visit window of  $\pm 30$  days (Table 1). Baseline data will be collected at Visit 1. In addition, COPD and chronic bronchitis participants will be contacted by phone on trimonthly basis within  $\pm 7$  days of the planned date to assess the CAT and to collect information on exacerbation rates and COPD medications; healthy controls will be contacted by phone on trimonthly basis within  $\pm 7$  days of the planned date to assess the CAT only. For the 4 clinic visits (V1-V4), all the participants should be clinically stable with no exacerbation or other acute medical event for at least 30 days prior to each scheduled visit.

A subset of participants will receive additional digital and biomarker assessments during the study. If moderate/severe exacerbations are reported by the participants or detected by the investigators during the acute phase of event, the participant will be invited to site hospital for an exacerbation visit. If multiple moderate/severe exacerbations are reported or detected, the participants will be contacted in consecutive manner for an exacerbation visit. The total number of the exacerbation visits should be no more than 2, with an interval of at least 21 days. Please note, for the sub-cohort, the planned clinic visits should be scheduled with an interval of at least 60 days after a completed exacerbation visit. When any participant in the sub-cohort is implemented an exacerbation visit, then his/her next planned clinic visit (V2-V4) should be scheduled at least 60 days after completing this exacerbation visit. In this case, the participant's clinic visit may be scheduled outside of the time window of  $\pm 30$  days, which will not be considered as a Protocol Deviation (for more information please refer to the Protocol Deviation Management Plan [PDMP] for this study).

**Table 1** Time and event table

| Protocol Activity                          | Screen/Baseline |               |               |               | Study visit |   |
|--|-----------------|---------------|---------------|---------------|-------------|---|
|  | V1              | V2            | V3            | V4            | EW          | Exacerbation visit ( $\le 2$ )  |
| visit                                      | M0              | M6            | M18           | M30           |             |   |
| Study month                                |                 |               |               |               |             |   |
| window                                     | +7 days         | $\pm 30$ days | $\pm 30$ days | $\pm 30$ days |             |   |
| Procedures                                 |                 |               |               |               |             |   |
| Informed consent               | X               | -             | -             | -             | -           | -   |
| Demography                                 | X               | -             | -             | -             | -           | -   |
| Medical history                            | X               | -             | -             | -             | -           | -   |
| Health and lifestyle information/Exposures | X               | -             | -             | -             | -           | -   |

| Protocol Activity   |                     | Screen/Baseline | Study visit |                                    |   |   |   |
|---|---------------------|-----------------|-------------|------------------------------------|---|---|---|
| Inclusion/Exclusion Criteria                                  |                     | X               | -           | -                                  | - | - | - |
| COPD and Exacerbation History                     |                     | X               | -           | -                                  | - | - | - |
| Concurrent medications  |                     | X               | X           | X                                  | X | X | - |
| Smoking status  |                     | X               | X           | X                                  | X | X | - |
| Spirometry                                        |                     | X               | X           | X                                  | X | X | X |
| Reversibility Testing   |                     | X               | -           | -                                  | - | - | - |
| Patient reported  | mMRC                | X               | -           | -                                  | - | - |   |
|   | SGRQ-C              | X               | -           | -                                  | - | - |   |
| Questionnaires  | CAPTURE             | X               |             | X                                  |   |   |   |
|   | CAT (on-site visit) | X               | X           | X                                  | X | - | X |
|   | CAT (Phone Call)    |                 |             | Trimonthly Phone Call  |   |   |   |
| Healthcare resource utilization and cost                      |                     | -               | X           | X                                  | X | X | X |
| Assessments  |                     |                 |             |                                    |   |   |   |
| COPD exacerbation assessment (on site visit)      |                     | -               | X           | X                                  | X | X | X |
| COPD exacerbation assessment (Phone Call)         |                     |                 |             | Trimonthly Phone Call  |   |   |   |
| COPD medication and treatment (on site visit)     |                     | X               | X           | X                                  | X | X | X |
| COPD medication and treatment (Phone Call)        |                     |                 |             | Trimonthly Phone Call  |   |   |   |
| Death   |                     | -               |             | X                                  |   |   |   |
| Serious Adverse Event assessment                 |                     |                 | X           | X                                  | X | X | X |
| Lab  |                     |                 |             |                                    |   |   |   |
| Blood Draw  for e.g. fibrinogen/hsCRP/Cell count |                     | X               | -           | -                                  | X | X | X |
| Sub-cohort only  |                     |                 |             |                                    |   |   |   |
| Lung HRCT scan                                    |                     | X               | -           | -                                  | X | X | X |
| Daily steps   |                     | X   | -           | X                      | - | - | - |
| Evening diary (EXACT plus additional questions)               |                     | X   | -           | X                      | - | - | - |

| Protocol Activity   | Screen/Baseline | Study visit     |   |                 |   |   |
|---|-----------------|-----------------|---|-----------------|---|---|
|   |                 | X  | - | X  | - |   |
| Monthly CAT   | X  | -               | - | X  | - | - |
| Blood biomarkers (inclusive of serum sRAGE, CC16, IP-10, HbA1c) | X               | -               | - | X               | X | X |
| Sputum cytology                                    | X               | -               | - | X               | X | X |
| Sputum microbiome                                  | X               | -               | - | X               | X | X |

CAT=COPD assessment test, COPD=Chronic Obstructive Pulmonary Disease, HRCT=High-resolution computed tomography, EW=Early Withdrawal, EXACT=EXAceration of COPD Tool; SGRQ-C=St.George's Respiratory Questionnaire for COPD. CAPTURE=COPD Assessment in Primary Care to Identify Undiagnosed Respiratory Disease and Exacerbation Risk

1. Exacerbation visits only apply to subjects included in the Biomarker & Digital sub-cohort. Moderate exacerbations are defined as COPD exacerbations that require either systemic corticosteroids (intramuscular (IM), intravenous, or oral) and/or antibiotics. Severe exacerbations are defined as COPD exacerbations requiring hospitalization or result in death.
2. Informed consent must be conducted at the screen visit prior to performing any study procedures.
3. For COPD participants only;
4. When a trimonthly telephone interview overlaps a clinical visit, the COPD exacerbation assessment, COPD medication and treatment questionnaires will be completed at the clinic visit. A month is defined as 30 days in this study.
5. Data collection of COPD exacerbation assessment, COPD medication and treatment are not required for the healthy control participants.
6. CT scan should only be performed at withdrawal visit if the last study CT performed was more than a year ago. Inspiratory and expiratory HRCT scans are required at Visit 1 and Visit 4, while only inspiratory scan will be conducted on exacerbation visit. The CT scan for an exacerbation visit should only be performed if the last study CT scan performed was more than 14 days.
7. Pre-and post- bronchodilator values of spirometry test will be collected at each site visit.
8. Physical activity will be evaluated by daily steps as assessed by a wrist band dispensed at baseline. Participants are required to keep wearing the wrist band for 1 month from Visit 1 (baseline) and Visit 3
9. Daily digital EXACT measurement for 6 months from Visit 1 (baseline) and Visit 3
10. Monthly digital measurement from baseline for 6 months, and monthly digital measurement from V3 for 6 months
11. Sputum can be collected spontaneously or can be induced, as per investigator judgement. Sputum sampling should only be done if, in the opinion of the investigator, it is safe for the subject. No systemic corticosteroids or antibiotics used within 14 days before collecting the sputum sample. Participants who do not have a qualified sputum cytology sample at baseline will be requested to have a sputum cytology sample taken or re-sampled at V2 (Note: for COPD participants, they should be clinically stable and has no exacerbations for at least 30 days prior to sampling).
12. Only SAEs relating to the study procedures are collected.
13. No systemic corticosteroids or antibiotics used within 14 days before collecting the blood sample.

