## Risk Assessment

| Potential Risk of Clinical Significance  | Summary of Data/Rationale for Risk   | Mitigation Strategy   |
|--|--|---|
| Investigational Product (IP)  |  |   |
| No investigational product (IP) will be investigated in this study; thus, detailed information on IP is not applicable | Not applicable  | Not applicable   |
| Study Procedures  |  |   |
| Potential risk for injury with phlebotomy  | Risks with phlebotomy include bruising, bleeding, infection, and nerve damage.   | 
 
Procedures to be performed by trained personnel (i.e., study nurse)
 
   |
| Potential risk for sputum induction  | Risks associated with sputum induction include worsened expiratory airflow limitation and oxygen desaturation  | 
 
Sputum induction to be conducted in sub-cohort participants only.
 
Procedures to be performed by trained personnel (i.e., study nurse).
 
A standardized sputum induction protocol to be applied which have minimal deleterious effects on lung function and oxygen saturation and safety checks during the procedure.
 
 |
| Subjects exposed to ionising radiation as a consequence of participation in this study.                                | 
The ionising radiation exposure comes from repeated low dose CT scans of the chest.
 
Participants with COPD will be subject to a maximum of 6 scans, resulting in an effective dose of ionising radiation in the range 10-16mSv. This is equivalent
 | The study has been designed to keep the radiation dose as low as reasonably practicable (ALARP) whilst obtaining images of sufficient quality to meet the objectives. Participants <50 years of age will not be included in the sub-cohort, nor will females of child bearing potential. Healthy control participants will be   |

| Potential Risk of Clinical Significance | Summary of Data/Rationale for Risk  | Mitigation Strategy   |
|---|---|---|

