#### 9.4. Adverse Events

No study drug will be given in this study, only study procedure related serious adverse events (SAE) will be recorded. All SAEs will be collected from the signing of the ICF until the follow-up visit at the time points specified in the SoA ([Table 1](#)).

The investigator is responsible for the detection and documentation of events meeting the criteria and definition of an SAE, provided in this protocol. During the study when there is a safety evaluation, the investigator or site staff will be responsible for detecting, documenting and reporting SAEs.

Adverse Events (AE) will not be captured in the study. It is possible that participants could spontaneously describe potential adverse events that occurred during the course of study visits. As part of the site orientation process, study team members will be trained in the recognition of potentially-reportable adverse events. If an AE (serious or non-serious) or complaint with any specifically named GSK product is reported spontaneously by a subject during the course of the study, the site staff will complete the AE reporting form and transmit the report to the GSK China within 24 hours of being made aware of the AE.

AE is any untoward medical occurrence in a patient or clinical investigation subject, temporally associated with the use of a medicinal product, whether or not considered related to the medicinal product. An AE can therefore be any unfavourable and unintended sign (including an abnormal laboratory finding), symptom, or disease (new or exacerbated) temporally associated with the use of a medicinal product. For marketed

medicinal products, this also includes failure to produce expected benefits (i.e., lack of efficacy), abuse or misuse.

Serious Adverse Event (SAE) is defined as any untoward medical occurrence that, at any dose:

- Results in death,
- Is life-threatening,
- Requires hospitalization or prolongation of existing hospitalization,
- Results in disability/incapacity,
- Is a congenital anomaly/birth defect?
- Other: medical or scientific judgement should be exercised in deciding whether reporting is appropriate in other situations, such as important medical events that may not be immediately life-threatening or result in death or hospitalisation but may jeopardise the subject or may require medical or surgical intervention to prevent one of the other outcomes listed in the above definition. These should also be considered serious.

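### No serious adverse event enquiry is scheduled at Visit 1, so harm from the first study procedures is first routinely sought at Month 6, and screen failures have no scheduled enquiry at all

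*Protocol*

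**What the plan says.** Protocol Section 2, Table 1 has a row headed "Serious Adverse Event assessment". It carries an X at V2, V3, V4, the early-withdrawal visit and the exacerbation visit, and nothing under Screen/Baseline (V1). The footnote to the row limits its scope: "Only SAEs relating to the study procedures are collected".

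Protocol Section 9.4 sets the collection period: "All SAEs will be collected from the signing of the ICF until the follow-up visit at the time points specified in the SoA". Consent is taken at V1, because footnote 2 of Table 1 requires that "Informed consent must be conducted at the screen visit prior to performing any study procedures".

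Protocol Section 9.6 states that the study schedules no safety assessment, which does not sit with a table that schedules one at five points.

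SAP Section 15.1 lists procedure-related SAEs in the Full Population. SAP Section 4 confines that population to people who were enrolled and attended Visit 1. It also defines an All Screened population of everyone who signed the consent form, used for the screen-failure summary.

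**The concern.** Only procedure-related SAEs are collected, so the time to ask about them is after the procedures. Visit 1 is one of the two scheduled visits with the fullest set of procedures, and it is the only column of the schedule without an SAE mark. V2 has the mark although it has no scheduled CT or routine blood draw.

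The protocol's own risk table says what could go wrong at Visit 1. For the blood draw, which everyone has: "Risks with phlebotomy include bruising, bleeding, infection, and nerve damage". For the sub-cohort: "Risks associated with sputum induction include worsened expiratory airflow limitation and oxygen desaturation". Some of these, such as infection or nerve damage, can become apparent after the participant has left the clinic. An enquiry five to seven months later relies on recall, and it asks the participant and the site to link an event to a procedure long past.

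Screen failures are a separate matter. A person can consent, have Visit 1 procedures, be excluded on the results and leave the study with no later visit or call.

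**Working it through.** No stated figure has to be reproduced. The check sets the passages side by side, with one piece of date arithmetic.

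1. **SAE row by column (Table 1).** V1: blank. V2, V3, V4, early withdrawal, exacerbation visit: X. That is five of six columns, with V1 the exception. The copies in SAP Section 17.2.1 and RAP Section 12.2.1 show the same pattern, so an error in reading the table is unlikely. Both copies carry older visit windows (+3 and ±28 days, against +7 and ±30 days in the current protocol). They repeat an earlier table and are not independent confirmation.

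2. **What is done at Visit 1.** All participants (about 2,000 planned): pre- and post-bronchodilator spirometry, a blood draw, and "Reversibility Testing", which is done at V1 only. Sub-cohort (400 planned): also "Lung HRCT scan", with inspiratory and expiratory scans, and sputum sampling, for which Section 9.2.9.2 prefers induction.

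3. **When the first routine enquiry falls.** Table 1 defines a month as 30 days. V2 is at 6 × 30 = day 180, with a window of ±30 days: 180 − 30 = day 150 to 180 + 30 = day 210. An early-withdrawal visit, or in the sub-cohort an exacerbation visit, can come sooner, and both carry the SAE mark.

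4. **Whether a call fills the interval.** The first three-monthly call is at 3 × 30 = day 90, ±7 days: day 83 to 97. Section 2 gives its content as the CAT, exacerbations and COPD medication for COPD and chronic bronchitis, and the CAT alone for healthy controls. Section 9.2.10 adds healthcare use, including hospitalisation with date and reason, and Section 9.2.11 adds deaths. None of these sections says that the caller asks whether an event was related to a study procedure.

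5. **Screen failures.** Section 6.2 expects some exclusions to follow the first CT scan, in all three groups. Section 6.4 lists the minimum data for a screen failure as demography, failure details and eligibility criteria, with no SAE item. Under SAP Sections 4 and 15.1 such a person is outside the Full Population, so a recorded SAE would not reach the planned listing.

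**The case against.** The strongest reply is that recording does not depend on the Visit 1 cell. Section 9.4 opens collection at consent and makes the investigator responsible for detecting and documenting SAEs. Section 9 sends immediate safety concerns to the sponsor as soon as the site is aware of them. Sputum induction is done by trained staff with safety checks, so acute harm would occur in front of the people who must report it. V2 can pick up earlier events in retrospect. All of this stands. A reader might infer that SAEs between Visit 1 and Month 6 go uncollected, or that reporting of events the site knows about is delayed. The documents do not support either.

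The calls are also not silent on serious events. Hospitalisation and death are SAE criteria, and Sections 9.2.10 and 9.2.11 can bring them to staff from the month-3 call. That stands as a partial safeguard. It is resource-use and vital-status data, it does not ask about cause, and Section 2 describes the healthy controls' calls as CAT only.

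Section 9.4 refers to a study pharmacovigilance plan for collection forms and processes, and that plan is not among the documents. It may deal with Visit 1 and with screen failures. But Section 9.4 points to the schedule for the time points, and the schedule gives none at Visit 1.

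Finally, a form completed on the day of Visit 1 would mostly record what staff had just seen. That is right: the form alone would not catch delayed harm, which is why the month-3 question is needed. The protocol also rates procedure risk as minimal, which bears on how many events to expect and leaves the mismatch in place.

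**Conclusion.** There is a gap in scheduled enquiry. Section 9.4 collects procedure-related SAEs from consent at the schedule's time points, and the schedule has none at the visit where consent is given and the procedures are first done. The first routine enquiry is at day 150 to 210, unless an early-withdrawal or exacerbation visit comes first. People who screen-fail after Visit 1 procedures have no scheduled enquiry and no place in the planned SAE listing.

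Two further readings go beyond the documents. A reader might infer that all of about 2,000 participants go unasked until Month 6, but early-withdrawal and exacerbation visits make that too absolute. A reader might also infer that procedure-related SAEs are the study's only safety outcome, but SAP Section 15.1 also summarises deaths and their causes.

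The conclusion assumes that the blank cell means no assessment, as the three tables agree, and that the pharmacovigilance plan does not schedule one. The documents give no basis for estimating how many events would be missed. The point is worth correcting because the correction is small, not because many missed events can be shown.

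**What to change.** - In Table 1, mark SAE assessment at V1, completed after the last V1 procedure and also for those who then screen-fail.
- Add one question on procedure-related SAEs to the month-3 call, for all arms including healthy controls. This is the step that captures delayed harm, and it brings the first enquiry after the participant leaves Visit 1 forward from day 150–210 to day 83–97.
- In SAP Section 15.1, list procedure-related SAEs for the All Screened population, which the SAP already defines.
- Reconcile Table 1, Section 9.4, Section 9.6 and the SAP copies of the schedule.

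If Visit 1 is already complete for everyone, extend the listing, reconcile the texts, and state in the report that harm from Visit 1 procedures was first routinely sought at Month 6.

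The cost is one form at a visit already held and one question on a call already made.
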